Official Title: Early neurological deterioration in recent small subcortical infarction: a multicenter prospective study

NCT number: not available

Date: December 25, 2022

Background and objectives

Recent small subcortical infarction (RSSI) is defined as a small deep infarction in the territory of a perforating artery with maximum axial diameters (MAD) of less than 20 mm. Although RSSI is generally considered to be of a relatively favorable prognosis, about 13.5% to 43% of RSSI patients experience early neurological deterioration (END) in the acute phase, which often bring adverse effects on long-term outcomes. Although a number of risk factors for END have been identified previously, however, the risk factors of END and the underlying etiological mechanism are still ambiguous, and also the relevant intervention measures lack sufficient evidences, which is a thorny problem that clinicians have to face.

In this multicenter, large-sample prospective registry study, the primary objective is to investigate the natural course of END in patients with RSSI. Exploring the risk factors and potential mechanism of its development, and trying to establish a comprehensive predictive model for END that integrates multi-dimensional information including clinical symptom, demographic data, biochemical biomarker and image data, and so as to provide a valuable tool for clinical evaluation and early management. Secondary objective is to figure the long term outcome of the patients with RSSI and its risk factors.

Methods

Study design

This study is a multicenter, consecutive, prospective, observational, cohort study recruiting RSSI patients within 72 hours after symptom onset. This study was approved by the Ethics Committee of The First Affiliated Hospital of Zhengzhou University. The anticipated duration of the study will be about 2 years from June 1, 2022 to June 1, 2024.

Study population

Inclusion criteria.

1. Age \geq 18 years;
2. Time from the last seen normal to enrollment \leq 72 h;
3. Completion of brain MRI (T1/T2/Flair/DWI/ADC sequences). The lesion belonged to the territory of the penetrating artery (lenticulostriate area and pons) on the DWI sequence and at least one of the vascular examinations such as MRA, CTA or DSA was completed.

Exclusion criteria.

1. Patients with low imaging quality affecting the evaluation of the results;
2. Intracranial hemorrhagic diseases, vascular malformations, aneurysms, brain abscesses, malignant space occupying lesions or other non-ischemic intracranial lesions observed by baseline head imaging;

3. Patients with combined malignancy, hematological disease and other systemic diseases with possible hypercoagulable state;
4. mRS score prior to the onset of the disease was ≥ 2 points;
5. Patients with symptom progression or TIA before completion of cranial MRI after admission;
6. Received or plan to receive acute endovascular treatment after onset of the disease;
7. Pregnant or lactating women;
8. Participation in another ongoing study;
9. Those who refused to participate in the study.

Data collection

RSSI patients within 72 hours of stroke onset were prospectively and consecutively enrolled from June 2022 to June 2023. After enrollment, Clinical data will be collected using an online electronic case report Form (e-CRF) at baseline and follow-up. Baseline data including demographic, first blood pressure, past and family history, past medications use, pre-stroke modified Rankin Scale score (mRS), assessment of mRS and NIHSS score on admission were recorded. After admission, NIHSS score was evaluated twice a day by two certified physicians, who were blinded to the study. laboratory tests including routine blood/biochemistry/renal function, etc.) Transthoracic echocardiogram, 24-hour Holter and neuroimages data including brain MRI/MRA/CTA/DSA, etc. were all

collected. During hospitalization, the drug therapy (antiplatelet/anticoagulation, lipid-lowering, glucose lowering, antihypertensive, etc.) were also recorded. Early neurological deteriorations (END) were monitored by two certified physicians, who were blinded to the imaging, and the primary outcome of our study was the occurrence of END, which was defined as any increase of ≥ 2 points in the total NIHSS score or ≥ 1 point on the motor items of the NIHSS within 7 days of hospital admission with blind evaluation. And any new cerebrovascular events confirmed during hospitalization were recorded. By face-to face or telephone interviews, we extended the follow up to 1 year for our secondary outcome as follow. The outcomes will be assessed by the neurologists blinded to study images. The quality control of all data will be held dynamically by the central center.

Outcome measures

Primary outcome

Any increase of ≥ 2 points in the total NIHSS score or ≥ 1 point on the motor items of the NIHSS within 7 days of hospital admission with blind evaluation.

Secondary outcome

1. percentage of patients with favorable functional recovery, defined as an mRS ≤ 1 ;
2. Percentage of patients with new vascular events, defined as any

- stroke (ischemic or hemorrhage);
3. Percentage of patients with the new clinical vascular events (ischemic stroke/ hemorrhagic stroke/ TIA/ MI/ vascular death) as a cluster and evaluated individually;
 4. Severe bleeding incidence (GUSTO definition), including fatal bleeding and symptomatic intracranial hemorrhage;
 5. Incidence of symptomatic and asymptomatic intracranial hemorrhagic events;
 6. All-cause mortality;
 7. cognitive function (MOCA/MMSE score).

Sample size

In our cohort study, no specific hypothesis for the primary outcome is set, the sample size is estimated based on the number of variables, using the method recommended for registry study (10 times number of variable). The sample size is estimated as 500 , and increases to 550 for 10% loss during follow-up.

Statistical analysis

Categorical variables will be presented as frequencies and percentages, Continuous variables with non-normal distributions will be shown as median and interquartile range (IQR), while continuous variables with normal distributions as mean and 95% confidence interval (CI). For the statistical significance analysis of different

groups and outcomes, Pearson χ^2 or Fisher's exact test, Wilcoxon tests, and t-tests will be used, where appropriate, with statistical uncertainty expressed by means of 95% CI. Cox proportional hazards model, Logistic regression model, and Poisson regression model will be used to assess the association between outcomes and predictors, where appropriate. All associated variables in the univariate analysis that reached $P < 0.10$ were included in the multinomial logistic analysis as candidate variables and then removed by a forward conditional selection. A two-sided $P < 0.05$ was considered statistically significant. The good prognosis is defined as 0–2 mRS score, and poor prognosis as 3–6 mRS score on 12 mon. All analysis will be performed using SPSS 26.0 (SPSS, Inc., Chicago, IL).

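### One-year vascular events are summarised as simple percentages despite 10% expected loss to follow-up, with no denominator rule and no estimator that handles censoring

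*Combined protocol and SAP*

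**What the plan says.** Under Data collection, the plan states that "we extended the follow up to 1 year for our secondary outcome as follow", by visit or telephone. No schedule of contacts within that year is given.

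Under Secondary outcome:
- Outcome 2 (any stroke) is worded "Percentage of patients with new vascular events, defined as any" stroke.
- Outcome 3 (the vascular cluster and its components) is worded "Percentage of patients with the new clinical vascular events".
- Outcomes 4 and 5 are "Severe bleeding incidence (GUSTO definition), including fatal bleeding and symptomatic intracranial hemorrhage" and "Incidence of symptomatic and asymptomatic intracranial hemorrhagic events".
- Outcome 6 is death from any cause. As with outcomes 4 and 5, no estimator is named.

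Under Sample size, "The sample size is estimated as 500", and this "increases to 550 for 10% loss during follow-up".

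Under Statistical analysis, categorical variables are summarised by counts and percentages. Cox, logistic and Poisson regression are listed for relating outcomes to predictors, and none is assigned to a particular outcome. The plan contains no Kaplan-Meier or cumulative incidence estimate, no censoring rule, and no statement of how lost patients enter a denominator.

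**The concern.** The secondary objective is the long-term outcome of these patients and its risk factors, so the one-year risks of stroke, other vascular events, bleeding and death are among the main figures the study will report. A patient last seen event-free at some point before 12 months has an unknown 12-month status. A simple percentage must either treat that patient as event-free, remove the patient, or remove some such patients and not others. Each choice gives a different figure from the same data, and the plan leaves the choice open until the data are in. The regression models do not close the gap: as planned, they yield associations, not an absolute 12-month risk.

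The case is clearest for outcomes 2 and 3, which are explicitly percentages of patients. For outcomes 4 to 6 the simple percentage is an inference from the general rule for categorical variables, because no other method of estimating absolute risk is named.

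**Working it through.** **Plan's own figure.** 500 × 1.10 = 550, which reproduces the stated size. Dividing instead, 500 / 0.9 = 556; the difference is immaterial here. Ten per cent loss from 550 leaves 550 × 0.9 = 495 patients with complete follow-up.

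**Inputs.** From the plan: loss of 10%, one-year follow-up, 550 patients. Assumed, because the documents give no event rates: true one-year risks R of 2%, 5%, 10% and 15%. Also assumed: constant hazards and, to begin with, loss independent of events. Administrative censoring is ignored, since enrolment to June 2023 and a study end of 1 June 2024 give nearly all patients a full year.

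**Formulas.** Event hazard λ = −ln(1 − R); loss hazard μ = −ln(0.9) = 0.1054.
- Proportion with an observed event: E = λ/(λ + μ) × (1 − exp(−(λ + μ))).
- Proportion lost while event-free: L = μ/(λ + μ) × (1 − exp(−(λ + μ))).

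**Three denominators.**
- (a) All enrolled, lost patients counted as event-free: E if loss is even over the year, 0.9R if all loss is at the start.
- (b) Only event-free lost patients dropped, observed events kept: E/(1 − L), with even loss.
- (c) All lost patients dropped: R, if loss is independent of risk.

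**Worked for R = 10%.** λ = μ = 0.1054, so exp(−(λ + μ)) = 0.9 × 0.9 = 0.81, and E = L = 0.5 × 0.19 = 0.095. Hence (a) is 9.5%, or 0.9 × 10 = 9.0% with early loss. For (b), 0.095/0.905 = 10.5%. For (c), 10.0%.

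| Assumed true risk | (a) even loss | (a) all early | (b) even loss | (c) |
|---|---|---|---|---|
| 2% | 1.90% | 1.80% | 2.11% | 2.00% |
| 5% | 4.75% | 4.50% | 5.26% | 5.00% |
| 10% | 9.50% | 9.00% | 10.50% | 10.00% |
| 15% | 14.26% | 13.50% | 15.71% | 15.00% |

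In relative terms, (a) is about 5% to 10% too low and (b) about 5% too high, at every risk level shown.

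**Loss related to risk.** Under (c), the risk among retained patients is R/(0.9 + 0.1k), where k is the risk in lost patients relative to retained ones. For R = 10%: k = 2 gives 10/1.1 = 9.1%, and k = 0.5 gives 10/0.95 = 10.5%.

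**Against sampling error.** The 95% half-width at 550 is 1.96 × √(R(1 − R)/550): 2.5 points at R = 10% and 3.0 points at R = 15%. Under (a) the shift is 0.5 to 1.0 point at 10% (20% to 40% of the half-width) and 0.7 to 1.5 points at 15% (about 25% to 50%).

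**The case against.** The strongest objection is that the documents do not show a bias in any particular direction. A reader might infer that every one-year incidence will be too low. That needs lost patients to stay in the denominator as event-free, which no section says. If anything, planning 500 and enlarging to 550 for loss suggests an analysis of about 500 completers, which is denominator (c) and roughly unbiased under independent loss. This stands, and the point is limited accordingly. It does not remove the problem: (c) is sound only if loss is unrelated to risk, and it discards the follow-up that lost patients did contribute.

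Two other inferences are tempting and should not be drawn.
- **Competing death as a fault of the percentage.** A crude proportion keeps patients who die of other causes in the denominator as non-events, as cumulative incidence also does. Competing death matters for the choice of replacement: 1 minus Kaplan-Meier with such deaths censored would overstate these events. Moreover, separate reporting of components is stated only for the vascular cluster in outcome 3, not for bleeding.
- **Conflict with the Cox results.** A hazard ratio and an absolute percentage are different quantities, so there is nothing that must agree.

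It is also fair to say that the 10% is a planning allowance rather than observed loss, and that the contact schedule is unknown. With a single contact at 12 months, lost patients would be censored near discharge, and Kaplan-Meier would come close to the completer percentage. The gain would then be smaller.

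**Conclusion.** The point holds in a limited form. The plan expects 10% loss over the year, states outcomes 2 and 3 as percentages of patients (and apparently treats outcomes 4 to 6 the same way), and names neither a denominator nor an absolute-risk estimator that uses partial follow-up. For an assumed true risk of 10%, the reported figure could run from 9.0% to 10.5% depending only on an unstated choice and the timing of loss, even when loss is independent of events. The direction is not fixed by the documents.

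The size is modest and lies within sampling error, but a confidence interval around the wrong percentage does not reveal the shift, and a larger sample does not remove it. The figures rest on assumed event risks, constant hazards for the even-loss case, and loss that actually reaches 10%. Only secondary outcomes are concerned. The change is worth making because it is cheap and fixes the choice before the data are seen.

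**What to change.** Add to Statistical analysis:
- For all-cause death, the 12-month Kaplan-Meier estimate with 95% CI.
- For any stroke, the vascular cluster and each of its components, and the bleeding outcomes, the 12-month Aalen-Johansen cumulative incidence with 95% CI. Death that is not itself part of the event is the competing event.
- Patients without the event and not known to have died are censored at last contact, or at 12 months if that comes first.
- Crude counts are kept as a supplement, with the denominator and the number lost stated.

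These estimators also assume that loss is independent of risk, so a short sensitivity analysis giving lost patients a higher or lower risk would be a useful addition.

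The cost is SAP wording, recording of event and last-contact dates on the e-CRF (needed anyway wherever Cox regression is used), and a little extra analysis. The cumulative incidence estimates may require software beyond base SPSS. Sample size and the primary analysis do not change.

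### The plan has no internal validation or shrinkage for the END predictive model, and a sample size of 10 patients per variable does not show that this model is adequately supported

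*Combined protocol and SAP*

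**What the plan says.** Background and objectives sets out the natural course of END as the primary objective and adds an aim of "trying to establish a comprehensive predictive model for END that integrates multi-dimensional information", intended to support clinical evaluation and early management. The same section gives the rate: "about 13.5% to 43% of RSSI patients experience early neurological deterioration (END) in the acute phase". It also has a long-term aim: "Secondary objective is to figure the long term outcome of the patients with RSSI and its risk factors".

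The Sample size section sets no hypothesis for the primary outcome. Instead, "the sample size is estimated based on the number of variables, using the method recommended for registry study (10 times number of variable". The result is "The sample size is estimated as 500 , and increases to 550 for 10% loss during follow-up". The number of variables is not given, and no END rate is used.

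On model building, Statistical analysis first applies a univariate screen at P < 0.10. It then says that the variables passing this screen "were included in the multinomial logistic analysis as candidate variables and then removed by a forward conditional selection". That sentence names no outcome. The section lists Cox, logistic and Poisson regression and ends with the software, SPSS 26.0. Nowhere does the document mention bootstrap, cross-validation, a split sample, external validation, shrinkage, calibration or a discrimination measure.

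**The concern.** END is a yes/no outcome, so the information for its logistic model depends on the number of END events. A rule of 10 patients per variable says nothing about that number until an END rate is supplied.

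Screening variables by P-value and estimating the survivors on the same data tends to retain noise variables and exaggerate coefficients. The model then looks better in the study data than it will in new patients: the apparent AUC is too high and the predictions are too extreme (calibration slope below 1). For a tool meant to guide early management, the reported performance could be materially too favourable, and nothing in the plan would reveal it.

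**Working it through.** **1. The plan's own figure.** 500 × 1.10 = 550, as stated (500/0.90 would give 556; the difference is immaterial). The 500 cannot be reproduced, because the variable count is missing. Solving backwards, 500/10 = 50 variables.

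**2. END events.** Inputs are N from Sample size and END rates from Background and objectives. Events = N × rate; events per variable = events / number of END predictors. Only 50 is implied by the plan; 30 and 20 are assumed alternatives.

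| | N = 500 | N = 550 |
|---|---|---|
| Events at 13.5%; 43% | 67.5; 215 | 74.25; 236.5 |
| Per variable, 50 END predictors | 1.35; 4.30 | 1.49; 4.73 |
| Per variable, 30 | 2.25; 7.17 | 2.48; 7.88 |
| Per variable, 20 | 3.38; 10.75 | 3.71; 11.83 |

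If every counted variable is an END predictor, the rule itself fixes the ratio on 500 patients at 10 × 0.135 = 1.35 to 10 × 0.43 = 4.3, whatever the count.

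Both denominators appear because the 10% allowance is for loss during follow-up, and Data collection says "we extended the follow up to 1 year for our secondary outcome as follow". END is assessed within 7 days of admission, so the number evaluable for END may lie anywhere from 500 to 550.

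**3. Precision of END incidence.** The 95% half-width is 1.96 × √(p(1−p)/n).
- n = 500: 1.96 × √(0.135 × 0.865/500) = 3.0 points; 1.96 × √(0.43 × 0.57/500) = 4.3 points.
- n = 550: 2.9 and 4.1 points.

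These figures ignore clustering by centre.

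**4. Optimism of the planned selection.** This was simulated with 5 true predictors, effects per SD, and the remaining variables noise. The screen was a univariate score test at P < 0.10, followed by forward entry at P < 0.05 and likelihood-ratio removal at P > 0.10. N was 550, and each fitted model was tested on new patients. The number of true predictors, effect sizes, correlations and entry and removal limits are assumptions; the documents give none of them. Variables are independent unless stated. Cells show apparent AUC / new-patient AUC / calibration slope.

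| Setting | 13.5% END | 43% END |
|---|---|---|
| 50 variables, log-odds 0.3 | 0.711 / 0.614 / 0.51 | 0.694 / 0.645 / 0.72 |
| 50 variables, log-odds 0.5 | 0.794 / 0.739 / 0.76 | 0.772 / 0.746 / 0.87 |
| 50 variables, log-odds 0.3, pairwise correlation 0.3 | 0.762 / 0.707 / 0.75 | 0.753 / 0.716 / 0.81 |
| 30 variables, log-odds 0.3 | 0.697 / 0.619 / 0.59 | 0.690 / 0.652 / 0.78 |
| 20 variables, log-odds 0.3 | 0.691 / 0.629 / 0.66 | 0.684 / 0.655 / 0.83 |
| 20 variables, log-odds 0.5 | 0.785 / 0.751 / 0.84 | 0.766 / 0.752 / 0.93 |

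The last row comes from 200 replicates, the others from 400. In the first row about 2.2 noise variables are retained on average, and 90% of fitted models contain at least one.

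AUC optimism therefore runs from 0.711 − 0.614 = 0.097 to 0.766 − 0.752 = 0.014.

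**5. Would bootstrapping the whole procedure help?** This used 50 variables, N = 550, and 120 replicates of 100 resamples. RMSE is measured against the new-patient AUC.

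| Log-odds, END rate | AUC apparent / corrected / new-patient | AUC RMSE, apparent → corrected | New-patient slope, before → after shrinkage |
|---|---|---|---|
| 0.3, 13.5% | 0.717 / 0.617 / 0.618 | 0.108 → 0.047 | 0.51 → 0.89 |
| 0.3, 43% | 0.695 / 0.628 / 0.647 | 0.055 → 0.038 | 0.73 → 1.09 |
| 0.5, 13.5% | 0.800 / 0.728 / 0.741 | 0.069 → 0.044 | 0.74 → 1.08 |
| 0.5, 43% | 0.772 / 0.728 / 0.746 | 0.034 → 0.032 | 0.87 → 1.10 |

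Correction lowers the error in all four settings, though barely in the last. Shrinkage brings the slope closer to 1 in all four, but overshoots in three.

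**The case against.** The best defence is that this is a registry with no hypothesis. Its primary objective is descriptive, and the document speaks only of trying to establish a model. That stands for incidence, which 500 patients estimate well. It does not excuse leaving unchecked a model that is meant for clinical use.

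A second defence is that the size of the problem is unknown. The 50 variables are back-solved, some may serve the 1-year outcome, and the selection sentence does not name END. With 20 END predictors, stronger effects and END near 43%, optimism is small. All of this stands. It limits how large the harm can be said to be, but not the absence of any step to measure it.

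A reader might go further and infer that the study is too small: ten END events for each of 50 variables would need 500/0.43 = 1,163 to 500/0.135 = 3,704 patients before loss. The documents do not support that. They do not say that there are 50 END predictors, and they adopt no events-per-variable requirement. Nor do they show that the model will be badly overfitted, since that depends on effect sizes and predictor numbers that they do not give.

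**Conclusion.** The point holds as a worthwhile and inexpensive improvement, centred on internal validation. As written, the plan could deliver an END prediction tool with only its apparent performance known. Under the assumed scenarios the overstatement ranges from large (50 variables, weak effects, 13.5% END: AUC about 0.10 too high, slope about 0.5) to small (20 variables, stronger effects, 43% END: AUC about 0.01 too high, slope about 0.93). The slope was below 1 in every setting tried.

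The sample-size part is narrower. The justification does not address END events and so does not show that the model is adequately supported. It does not follow that 550 is wrong.

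The conclusion rests on reading the selection rule as applying to the END model, which is likely but not stated, and on the cited END range holding in this cohort. That range comes with no END definition, and patients whose symptoms progress before MRI are excluded, so the actual rate may differ.

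**What to change.** Keep 550 patients.

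1. Add to Statistical analysis, before END is analysed:

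> The full END model-building procedure (univariate screen plus forward selection) will be repeated in bootstrap samples. Optimism-corrected AUC and calibration slope will be reported with the apparent values, and coefficients multiplied by the bootstrap slope will be reported alongside the unshrunken ones.

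Name the software if it is not SPSS 26.0.

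2. Restate the Sample size justification on one denominator, for example:

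> If the END rate is 13.5% to 43%, 500 evaluable patients give about 68 to 215 END events and a 95% CI half-width for END incidence of 3.0 to 4.3 points (ignoring centre clustering).

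State how many of the counted variables are candidate END predictors. The sponsor should also confirm whether the 10% loss applies to the 7-day END assessment or only to the 1-year follow-up.

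The cost is wording and bootstrap programming, with no extra patients. There are downsides:
- Reported performance will be less favourable.
- The corrected AUC can be too low by about 0.01 to 0.02.
- Uniform shrinkage can overshoot (slope about 1.05 to 1.10), which is why both sets of coefficients should be shown.
- Where optimism is already small there is almost no gain: with 20 variables, log-odds 0.5 and 43% END, correction did not reduce the AUC RMSE (0.024 versus 0.025).

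### The enrolment figure of 550 leaves 495 patients, not 500, after the stated 10% loss: a minor arithmetic correction

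*Combined protocol and SAP*

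**What the plan says.** The Sample size section opens by stating that "no specific hypothesis for the primary outcome is set". The number is instead derived "using the method recommended for registry study (10 times number of variable"; how many variables that means is not given. The result follows: "The sample size is estimated as 500", and this figure then "increases to 550 for 10% loss during follow-up". No inflation formula is written, and the section does not say which analysis the 500 is meant for.

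Two other statements show where loss would be felt. The primary outcome, END, is assessed "within 7 days of hospital admission with blind evaluation" (Outcome measures, Primary outcome). The longer observation period serves the other outcomes: "we extended the follow up to 1 year for our secondary outcome" (Data collection).

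**The concern.** An allowance for loss is meant to let the target number survive the assumed loss. Loss during follow-up is ordinarily a fraction of the patients who were enrolled and followed. On that basis the target is divided by the proportion retained. Multiplying the target by one plus the loss rate always gives too small a number, because the loss is then taken from the larger, inflated total. The 550 looks like the product of that shortcut.

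What is at stake is modest. A reader who takes the 500 and the 10% at face value will expect 500 patients with 1-year data, and the stated enrolment does not provide them. The 500 and the 550 are the figures by which recruitment and retention will be reported, so they should agree with each other.

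**Working it through.** **Inputs, all from the Sample size section**

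- Target before allowance for loss: n = 500
- Assumed loss during follow-up: d = 10% = 0.10
- Stated enrolment after the allowance: 550

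**Step 1. Reproduce the plan's figure.**
n × (1 + d) = 500 × 1.10 = 550. This matches exactly. The plan writes no formula, so the multiplication is inferred from the match; the next steps do not depend on that inference.

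**Step 2. Patients remaining if 10% of those enrolled are lost.**
550 × (1 − 0.10) = 550 × 0.90 = 495.
Shortfall: 500 − 495 = 5 patients, and 5/500 = 1.0%.

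**Step 3. Enrolment that would keep 500.**
n/(1 − d) = 500/0.90 = 555.6, rounded up to 556.
Check: 556 × 0.90 = 500.4, which is at least 500.
Difference from the plan: 556 − 550 = 6 patients, and 6/550 = 1.1%.

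**Step 4. The loss that 550 can absorb.**
(550 − 500)/550 = 50/550 = 9.1%. Up to that loss 500 remain; at 10% they do not.

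**Step 5. Which outcomes are exposed.**
END is scored in the first 7 days after admission, with the NIHSS assessed twice a day. The 1-year interviews, face to face or by telephone, serve the secondary outcomes. Loss during follow-up therefore falls mainly on the secondary outcomes and should leave the primary outcome largely unaffected.

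**The case against.** The strongest reply is that nothing depends on 5 patients. The 500 comes from a rule of thumb and not from a power or precision calculation, the 10% is a round planning figure with no stated source, and the section calls 500 an estimate and not a required minimum. Enrolment is consecutive over a calendar window, June 2022 to June 2023, and nothing in the plan says that recruitment stops at 550. All of this stands, and it is why the point is minor. It does not make 550, 500 and 10% consistent with one another.

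A second reply is that the 10% might mean 10% of the target, that is 50 patients, in which case 550 is exact. The plan does not define the loss that way. If it was intended, the text should say so, and the equivalent statement is that about 9% of those enrolled may be lost.

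A reader might also infer more than the documents support:

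- *That the primary analysis falls short of 500.* It need not. The allowance is for loss during follow-up, while END is assessed within 7 days, when up to 550 patients could contribute.
- *That the END analysis will use every enrolled patient.* The plan does not say this. It defines no analysis set for END and does not say how discharge or withdrawal before day 7 is handled.
- *That the plan breaks its own rule because 495 patients over 50 variables gives 9.9 per variable.* The 50 is only back-calculated as 500/10; the plan never states the number of variables and does not say that the rule was set for the 1-year outcomes. The ratio also counts patients and not events, so the step from 10 to 9.9 is not informative.
- *That 500 and 550 are the only planning figures.* They are not: the Background section gives an END incidence of 13.5% to 43%, and the Statistical analysis section sets a two-sided significance level of 0.05.

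**Conclusion.** The sentence is wrong as written, and the correction is minor. With 550 enrolled and 10% of them lost, 495 remain; 10% loss would need 556, and 550 keeps 500 only for a loss of up to 9.1%. The gap is 5 retained or 6 enrolled patients, about 1%. No other part of the plan corrects it.

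The conclusion rests on one assumption: that the 10% is a proportion of the patients enrolled, which is the usual meaning and is not contradicted in the text.

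The effect is confined mainly to the 1-year secondary outcomes. Since the plan states no hypothesis, power or precision target, no such figure changes, and the point gives no reason to doubt the study's findings on END.

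**What to change.** Rewrite the last sentence of the Sample size section in one of two ways, both of which keep enrolment at 550:

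- state that 550 enrolled patients leave about 495 at 1 year after a 10% loss; or
- state that 550 allows for about 9% loss during follow-up from a target of 500.

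If the sponsor prefers to keep both the 500 and the 10%, the matching enrolment is 556, but the size of the gap does not require this.

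The cost of either rewrite is one sentence. No patients are added, and no analysis changes.
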